#### THE HYPOTHESES TO BE TESTED ARE:

- The knee joint torques generated by fatigue delaying stimulation paradigms will be sufficient to keep the knees locked during standing for at least 10 minutes. This will be tested by tracking how long the knee can produce an extension torque on the dynamometer that exceeds a threshold set for each subject based on their body weight. [5.]
- Standing with fatigue delaying stimulation paradigms will be more stable and of longer duration
  than constant stimulation. This will be tested by recording the elapsed standing times before
  system users are required to sit due to fatigue of the quadriceps muscles for each of the
  advanced stimulation waveforms, as well as by monitoring variations in knee angle and
  subjective impressions of stability while standing.
- Clinical performance of the fatigue delaying stimulation paradigms will be stable over time. This
  will be tested by repeating the tuning procedures and comparing the optimal parameters over
  time, repeating dynamometer testing of the same stimulus paradigm at various time intervals,
  and repeating stand-to-fatigue, body weight distribution and stability tests in the laboratory.
- Objective optimization of control parameters will lead to longer sustained contractions before
  fatigue. This will be tested by comparing the knee extension torque produced by hand tuning the
  stimulation paradigms to the outcome applying the automated and objective optimization
  process for setting up stimulus parameters. These experiments can be performed primarily on
  the dynamometer and verified during standing in the laboratory.

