## 10. Describe the means of analyzing the data and evaluating the results.

- State the anticipated methods to be used for analysis and interpretation of the data.
- The methods must compliment the design of the study and the nature of the data which is being collected.

This study takes the form of a case series and employs the principles of single-subject research design. Each subject acts as his or her own concurrent (differences among stimulation paradigms for the individual at the same time interval) and longitudinal (initial post-exercise and training measurement versus follow-up values) controls. Primary statistical analyses will be in

comparison to the continuous stimulation case and will be performed on each subject individually. The effect sizes for these analyses were estimated using data obtained from existing 8-channel users and assuming a power level of 80%.

- 1. The longitudinal stability of the optimal stimulation parameters (pulse width and amplitudes) to ensure selective and non-overlapping activation of different muscles with each contact within the nerve cuffs will be assessed via a two-tailed t-test between initial and follow-up measurements.
- 2. Differences among the fatigue-delaying stimulation paradigms (carousel, interleaved, sum of phase-shifted sinusoid) and in comparison to continuous stimulation in terms of biomechanical measures of fatigue (T50, T0.21) and isometric strength will be determined by ANOVA performed on repeated measures of the outcome variables at each measurement interval.
- 3. Standing performance in terms of elapsed standing time and body weight distribution on the arms and legs will be compared across stimulation paradigms for each subject via ANOVA.
- 4. Standing stability in terms of variations in knee joint angle and location of body center of mass while standing with various stimulation paradigms will be assessed via ANOVA. The Wilcoxon Ranked Sum Test will be applied to the seven point ordinal data related to the subjective impressions of stability.

Tests will nominally be repeated three times in random order and the resulting body weight distribution and elapsed standing durations will be compared via ANOVA to determine the relative performance of each stimulation paradigm.

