#### Testing and Experimentation (Phase III):

Once training is completed, the subject will commence with the testing phase to assess the performance of the implanted system.

Implementation of the fatigue delaying paradigms is essentially a three-step process.

- 1.) Stimulation parameters must be chosen to produce strong muscle contractions with little or no overlap in the populations of motor units activated. This step will be accomplished with the subject positioned in a dynamometer while stimulation parameters are varied by a computer-controlled optimization algorithm to create non-overlapping recruitment curves. [6].
- 2.) Using the values that specify non-overlapping stimulation as an upper limit, patterns must be tuned to produce the desired profile of joint torque, such as ramping up, plateau time, and ramping down for carousel stimulation, or sinusoidal oscillation frequency and pulse width values for the SOPS paradigm. For the carousel and SOPS paradigms, it is important to ensure that the maximum joint torques generated by stimulating through individual contacts are balanced and roughly equivalent to each other to avoid ripple (jitter or oscillations) in the output when they are combined.
- 3.) Joint torque will be recorded on the dynamometer during each stimulation pattern and ripple will be quantified to ensure that a constant contraction is achieved.

These three steps can be completed in approximately five two-hour long sessions.

Biomechanical Tests Strength and Endurance: Once stimulation patterns have been hand-tuned to produce strong, low-ripple contractions for each of the fatigue delaying stimulation regimes, tests of their functional impact on fatigue will be performed. To quantify the rate of fatigue of each paradigm isometric fatigue tests will be performed on the dynamometer with the knee held in 20° of flexion. Each fatigue test will consist of approximately 30 minutes of stimulation with a particular paradigm. Fatigue tests for all four conditions (SOPS, carousel, interleaved and baseline continuous stimulation) will be repeated for both legs nominally three times in random order for each subject, with never more than one fatigue test per leg per day.

Standing Time and Body Weight Distribution:

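### Analysis 1 tests only the signed mean change in stimulation parameters, with unit and pairing unstated, so opposite drifts of individual contacts can cancel unseen

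*Combined protocol and SAP*

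**What the plan says.** The third hypothesis in Item 9 reads: "Clinical performance of the fatigue delaying stimulation paradigms will be stable over time". One of its tests consists of "repeating the tuning procedures and comparing the optimal parameters over" time. The others repeat the dynamometer tests and the laboratory tests of standing, weight distribution and stability.

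Item 10, analysis 1 turns the parameter part into a named method. Its subject is "The longitudinal stability of the optimal stimulation parameters (pulse width and amplitudes"), its purpose is "selective and non-overlapping activation of different muscles with each contact within the nerve cuffs", and the stability "will be assessed via a two-tailed t-test between initial and follow-up measurements".

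Four things that determine what this test can show are not given:

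- **Unit.** Item 10 does not say whether the replicates are contacts within a subject, repeats at one contact, or subjects. The statement that analyses are in "comparison to the continuous stimulation case and will be performed on each subject individually" concerns the primary analyses. Analysis 1 is not a comparison with continuous stimulation, so the reach of that sentence is unclear.
- **Pairing.** Paired or unpaired is not stated.
- **Replication of tuning.** In Item 10, "Tests will nominally be repeated three times in random order" is tied to weight distribution and standing time. Item 13 (Testing and Experimentation, Phase III) plans three repeats of the fatigue tests. For tuning it says only: "These three steps can be completed in approximately five two-hour long sessions".
- **Tolerance.** There is no absolute change, agreement measure, per-contact band or equivalence margin. The Discharge and Follow-up text adds a comparison with the pre-discharge baseline, without a metric.

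**The concern.** The property of interest belongs to each contact: it should keep activating its own motor unit pool without spilling into its neighbour's. A stability measure should therefore show how far each contact's tuned values have moved. A t-test on initial and follow-up values asks something else, namely whether the average has shifted. If some contacts need more charge and others less, the average can stay still while individual settings have changed a great deal.

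At stake is the meaning of a non-significant result. Under a hypothesis of stability over time it would naturally be reported as support, when it may say little about the contacts.

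**Working it through.** **1. The plan's own figure.** There is none for analysis 1. The 15 new subjects and 80% power in Item 11 rest on standing time, body weight support and knee torque, and no alpha, effect size, SD or contact count is given. Everything below assumes two-sided alpha 0.05 and illustrative contact counts and drifts.

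**2. What the test measures.** With change d at each of K contacts, the paired statistic is t = mean(d) / (SD(d)/√K). The numerator is the signed mean. Opposite changes shrink it and also inflate the denominator.

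**3. Worked example.** Take K = 8 with changes alternately +30% and -30%.
- mean(d) = 0; SD = √(8 × 30² / 7) = 32.1; SE = 32.1/√8 = 11.3; t = 0; p = 1.
- The mean absolute change is 30%.
- On the log scale (ln 1.3 = 0.262, ln 0.7 = -0.357) the mean is -0.047 and the SD 0.331, so t = -0.047/(0.331/√8) = -0.40, p = 0.70. Taking logs alone does not help.

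**4. Simulated rejection rates, contacts pooled within one subject, paired t, K = 8** (40,000 runs per cell; D is the drift per contact in SDs of the noise in a change):

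| D | half up, half down | all one way | random signs |
|---|---|---|---|
| 0 | 5.0% | 5.0% | 5.0% |
| 1 | 0.7% | 68% | 5.2% |
| 2 | <0.1% | 99.7% | 5.5% |
| 3 | <0.1% | 100% | 6.1% |
| 5 | <0.1% | 100% | 6.5% |

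At D = 3, by split of the eight contacts: 5:3 below 0.1%, 6:2 about 2%, 7:1 about 75%, 8:0 100%. With random signs over D = 1 to 5, 4 contacts give 6% to 13% and 16 contacts 5% to 6%.

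**5. Symmetric random drift** (50,000 runs per cell). For SDs of 2%, 20% and 50% and K = 4, 8 and 16, the paired test rejects in 4.8% to 5.2%. With 15 pooled subjects it rejects in 5.0% to 5.1%. An unpaired test with a 40% spread between contacts (K = 4 or 8) rejects in at most 1.6%.

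**6. Testing each contact separately.** Contacts then cannot cancel each other. Assuming three tunings per visit, power at drifts of 2, 3 and 5 SDs of one measurement is 46%, 78% and 99% unpaired, or 29%, 51% and 84% paired. With one tuning per visit there is no within-visit variance and this test cannot be computed.

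**7. A sign-free summary.** For K independent log ratios centred at zero, the 95% CI for the root-mean-square (RMS) is the estimate times √(K/χ²). With K = 8 the factors are √(8/17.53) = 0.675 and √(8/2.18) = 1.916. In the example of step 3, RMS = √((0.262² + 0.357²)/2) = 0.313, a typical factor of e^0.313 = 1.37. Its CI is 0.211 to 0.600, or factors of 1.24 to 1.82. The drift that gave p = 1 is now visible.

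**The case against.** **The unit is inferred.** The plan never says that contacts are pooled, and silence on repeat tuning is not a rule against it. That stands, and the point is conditional for that reason. However, a test per contact needs repeat tunings that the plan does not describe. Pooling subjects only moves the cancellation from contacts to subjects.

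**The drift pattern is assumed.** A test of the mean must reject at about 5% when drift is centred on zero, so the simulations show how the test behaves and do not predict this trial. The risk section of the protocol names mechanisms that could push mostly one way, such as nerve compression weakening the muscle response or an electrode moving away from its nerve. Drift of that kind would be detected (step 4). This also stands.

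**A rise and a fall need not be equivalent.** Phase III treats the non-overlapping values as an upper limit, so the direction of a change can matter for selectivity. A purely sign-free summary would hide that. The sign should therefore be reported for each contact alongside the size.

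**An equivalence margin might be enough.** A reader might infer that an equivalence test on the same mean would be fooled as well. In general it would not, because opposite drifts widen the interval. In the example the 90% CI is ±1.895 × 11.34 = ±21.5%, so equivalence fails at any tighter margin. A margin would help, but the plan has none, and the mean still does not show which contacts moved or how far.

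**Other evidence exists.** Repeat dynamometer and standing tests also bear on the third hypothesis, and recruitment properties and stimulus thresholds are to be measured again. This limits the consequence but does not mend analysis 1.

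**Conclusion.** The point holds in conditional form. As written, analysis 1 measures only the signed mean change, and its unit and pairing are unstated. If contacts are pooled within a subject, or subjects are pooled, drifts in opposite directions can cancel, and a non-significant result says little about how far individual contacts moved. Under balanced opposite drift of two or more noise SDs over eight contacts, rejection falls below 0.1%. Under symmetric random drift the paired test stays near 5% whatever the drift SD. Drift that is mainly one-way (7:1 or 8:0 in the example) is found. These figures rest on the assumed alpha, contact numbers and drift sizes.

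Analysis 1 is the only named statistical test of the tuned parameters, but not the only evidence on the third hypothesis. A reader might go on to infer that the trial will conclude that one clinic tuning suffices. The documents neither plan nor imply that conclusion, and it is no part of this point. The change is worth making, but it does not touch the primary comparisons or the sample size.

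**What to change.** Amend Item 10, analysis 1 as follows:

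- State the unit of analysis, and pair initial with follow-up values by contact.
- For each contact, report log(follow-up/initial) for pulse width and for amplitude, with its sign.
- Per subject, report the RMS (or mean absolute) log ratio with a 95% CI, and the number of contacts outside a band that the investigators fix before follow-up data are seen.
- Keep the signed mean change as a secondary description of systematic shift.
- State that a non-significant t-test will not be read as stability.

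The cost is analysis-plan wording; the tuning values are already to be collected and no visit is added. There are two limits to report openly. With few contacts the interval is wide: 0.68 to 1.92 times the estimate for an assumed eight, and that calculation also assumes independent, zero-centred log ratios. A sign-free summary is also not zero when nothing drifts: in the simulation the mean absolute change was 0.80 noise SDs with no drift, against 3.0 at D = 3. The band should therefore be set with the repeatability of tuning in mind.

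### Comparison with continuous stimulation is primary, but the only test named for the measured outcomes is an ANOVA across four conditions with no contrast against continuous

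*Combined protocol and SAP*

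**What the plan says.** The primary comparison is clear. Item 10 says that the primary statistical analyses are in "comparison to the continuous stimulation case and will be performed on each subject individually". The second hypothesis in item 9 gives it a direction: "Standing with fatigue delaying stimulation paradigms will be more stable and of longer duration" than constant stimulation.

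The tests named in item 10 for the measured outcomes are:

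- Analysis 2 (fatigue measures and isometric strength): ANOVA on repeated measures. Its aim covers differences among the new paradigms and also differences "in comparison to continuous stimulation in terms of biomechanical measures of fatigue" and strength.
- Analysis 3 (standing time and body weight distribution): these "will be compared across stimulation paradigms for each subject via ANOVA".
- Analysis 4 (knee angle and centre of mass): ANOVA. The ordinal stability rating is treated separately ("The Wilcoxon Ranked Sum Test will be applied to the seven point ordinal data related to the subjective impressions of stability") and is outside this point.

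Item 13 (Testing and Experimentation, Phase III) lists four conditions for the fatigue tests: three fatigue-delaying paradigms and continuous stimulation. On replication, item 10 says "Tests will nominally be repeated three times in random order". Item 13 adds that the fatigue tests "will be repeated for both legs nominally three times in random order for each subject".

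No contrast, post-hoc procedure, alpha or multiplicity rule is given for these analyses. Sidedness is stated only for analysis 1.

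**The concern.** The overall F from a four-level ANOVA tests whether all four means are equal. The primary question is whether a given paradigm is better than continuous. F can be significant because the new paradigms differ from each other, or because one is worse than continuous. It carries no direction and names no paradigm.

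If the ANOVA result is taken as the primary result in each subject, a significant finding could be reported as support for the second hypothesis when no paradigm helps. If the analyst goes beyond F, the plan leaves open which comparisons to make and how to adjust them, so that choice could be made after the data are seen.

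**Working it through.** **The plan's own figure.** Item 11 gives 15 new subjects at 80% power. This cannot be reproduced, because no effect size, SD, alpha or test is stated. The check below concerns the analysis within one subject.

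**Inputs.** Four conditions (item 13) and n = 3 tests per condition (items 10 and 13), so 12 observations and 12 − 4 = 8 error df per subject. Assumed, because the documents do not give them: alpha 0.05, two-sided contrasts, independent normal errors, and effects of 2 to 2.5 within-subject SDs. The ANOVA is read as one factor with four levels.

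**Overall F.** Power comes from the noncentral F(3, 8) with λ = n Σ(μᵢ − μ̄)², means in SD units.

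- One paradigm 2.5 SD worse, the others equal to continuous: means (0, 0, 0, −2.5) and μ̄ = −0.625. The sum of squares is 3 × 0.625² + 1.875² = 4.6875, so λ = 3 × 4.6875 = 14.06. Power is 69%.
- All three 2.5 SD better: means (0, 2.5, 2.5, 2.5) and μ̄ = 1.875. The sum of squares is 1.875² + 3 × 0.625² = 4.6875, so λ is again 14.06 and power is again 69%.

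F therefore behaves identically when the hypothesis is true of every paradigm and when it is true of none.

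**Contrast with continuous.** For each paradigm, t = (paradigm mean − continuous mean) / √(2·MSE/n). The two-sided 5% Dunnett critical value for three comparisons on 8 df, by simulation, is about 2.88. The last column below is the simulated chance that at least one paradigm is declared better than continuous.

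| True pattern | Overall F significant | Dunnett: some paradigm better |
|---|---|---|
| One 2.5 SD worse, two equal to continuous | 69% | 2% |
| One better and one worse by 2 SD | 91% | 39% |
| All three better by 2 SD | 49% | 59% |
| All three better by 2.5 SD | 69% | 78% |
| Only one better, by 2 SD | 49% | 39% |
| Two better, by 2 SD | 62% | 52% |

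The first two rows show the mismatch. The last four show that F has no consistent advantage or disadvantage in power. The columns also answer different questions, since F does not identify a paradigm.

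**Gating by F.** If Dunnett is applied only after a significant F, the chance of declaring a paradigm better at 2 SD falls from 59% to 49% (all three work), from 39% to 36% (one works) and from 52% to 49% (two work).

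**Fatigue tests with legs pooled (assumption).** Six tests per condition give 24 − 4 = 20 error df. With one paradigm 2 SD worse, the sum of squares is 0.75 × 2² = 3, λ = 6 × 3 = 18, and F is significant in 91% of subjects although none is better. More replication makes F more sensitive but does not make it answer the primary question.

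**The case against.** The strongest reply is that ANOVA can carry planned contrasts. Item 10 names comparison with continuous as primary, and analysis 2 repeats it. A reader might infer that the plan adopts the overall F as its decision rule. The text does not say so; that reading rests only on the absence of any named contrast. This much stands: the plan leaves the test of its primary comparison open rather than stating a wrong one. But analysis 2 attaches no procedure to the comparison, and analyses 3 and 4 do not mention continuous stimulation.

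A reader might also infer that the F-test wastes power. That holds only when the paradigms help to a similar degree. When one or two work, F rejects more often than Dunnett, and the documents give no effect size or SD from which to choose a pattern.

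A third tempting reading is that the plan inflates false positives. Three unadjusted t-tests against continuous would give a familywise error of about 12% per subject and outcome, but the plan does not propose them.

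Comparing the new paradigms with each other is also a stated aim, in analysis 2 and in the closing sentence of item 10, and an overall test partly serves it. Finally, this is a single-subject case series in an ethics form that asks for anticipated methods. That lowers the detail to be expected, but it does not settle which result answers the primary question.

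**Conclusion.** The concern holds as a mismatch between the primary comparison and the named test. For the ANOVA outcomes in analyses 2 to 4, a significant result does not show that any paradigm outperforms continuous stimulation. In the illustrative case, F is significant in about 69% of subjects when none is better, against about 2% for a positive Dunnett result.

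These percentages rest on three tests per condition, 8 error df, alpha 0.05 and an assumed effect of 2.5 SD. The logical point does not depend on them. The documents support neither a general loss of power nor an inflated error rate. The change should be made, because a better-matched test is available from the same data.

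**What to change.** In item 10, for the ANOVA outcomes in analyses 2 to 4:

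- Make the decision test each fatigue-delaying paradigm versus continuous stimulation, Dunnett-adjusted on the ANOVA error term. The critical |t| is about 2.88 on 8 df at two-sided 0.05; recompute it if replication differs or legs are pooled.
- State alpha and sidedness.
- State that these comparisons are gated neither by the overall F nor by a contrast averaging the three paradigms. The averaged contrast has 75% power if all three are better by 2 SD, but only 14% if one is, so as a gate it could hide a single effective paradigm.
- Keep the overall F and the comparisons among the new paradigms as secondary.

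This costs plan wording and no additional standing or fatigue tests. The price is power relative to unadjusted pairwise tests: with three tests per condition, 80% power for one given paradigm needs a difference of about 3.12 SD with Dunnett, against 2.61 SD unadjusted.

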## 11. Provide a BRIEF DESCRIPTION of how the estimated number of study subjects needed for this research was determined

- If this is a quantitative study provide the method of determining sample size estimates.
- If multiple studies are planned provide a power analysis or justification for each one.

The number of new subjects (15) to be enrolled in this project and receive implanted neuroprostheses was based on the effect size and variability observed in previous measurements of the outcomes of interest (elapsed standing time, body weight support, knee extension torque) and an assumed power level of 80%. The timing of recruitment and enrollment is based on the time required to fabricate implanted electrodes and stimulators, as well as the time required for implanting, training and testing the subjects who receive the devices. In addition, 10 existing subjects who had already received their implanted systems while enrolled in other approved protocols will be eligible to volunteer for the testing and experimentation portion of the study.

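### Item 11 rests the 15 implanted subjects on 80% power, but Item 10's primary analyses are run within each subject, where power does not depend on the number of subjects, and no across-subject test is clearly specified

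*Combined protocol and SAP*

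**What the plan says.** Item 11 gives the basis for the sample size: "The number of new subjects (15) to be enrolled in this project and receive implanted neuroprostheses was based on the effect size and variability" in previous measurements of three outcomes, "elapsed standing time, body weight support, knee extension torque) and an assumed power level of 80" percent. It adds that "10 existing subjects who had already received their implanted systems while enrolled in other approved protocols will be eligible to volunteer" for the testing phase; these 10 are not part of the sizing statement.

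Item 10 describes the analysis: "This study takes the form of a case series and employs the principles of single-subject research design". The primary analyses are in "comparison to the continuous stimulation case and will be performed on each subject individually". The next sentence reads: "The effect sizes for these analyses were estimated using data obtained from existing 8-channel users and assuming a power level of 80" percent.

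The unit of each listed analysis is as follows.

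- Analysis 1 (t-test on stability of stimulation parameters): none named.
- Analysis 2 (fatigue measures and isometric strength): "ANOVA performed on repeated measures of the outcome variables at each measurement interval"; none named.
- Analysis 3 (standing time and body weight distribution): "will be compared across stimulation paradigms for each subject via ANOVA".
- Analysis 4 (knee angle, centre of mass, stability ratings): none named.
- Closing sentence of Item 10 (nominally three repeats in random order, ANOVA): none named.

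Item 13, under Testing and Experimentation (Phase III), has four conditions: three fatigue-delaying paradigms and continuous stimulation. Dynamometer fatigue tests are done on both legs, nominally three times each. Item 8 gives a separate reason for 15: showing that the approach is useful and generalizable.

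**The concern.** Item 11 presents 15 as the output of a power calculation. A power calculation that yields a number of subjects needs a test in which subjects are the replicates. In the primary analyses of Item 10 the replicates are repeated trials in one person. Enrolling more people gives more such tests but does not make any one of them more powerful.

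The number of people who undergo implant surgery is thus justified to the IRB by a power figure that the stated primary analyses do not draw from that number. A reader cannot tell what difference the study can detect, either within one subject or across the 15. The hypotheses in Item 9 and the generalizability aim in Item 8 are general claims, yet no rule is given for combining 15 separate results into an answer to them.

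**Working it through.** **Inputs from the documents.** 15 new subjects, 10 existing recipients and 80% power (Item 11); nominally 3 repeats (Item 10); 4 conditions, and both legs on the dynamometer (Item 13).

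**Inputs not given.** Alpha, effect size, SD and the test behind the 15. I assume a two-sided 5% level, independent repeats and a common within-subject variance, and express differences in SD units.

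**Step 1. Can the 15 be reproduced?** No, because the inputs are not printed. For a paired t-test across subjects at 80% power, the required number depends on the standardised paired difference d:

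| d | 0.5 | 0.6 | 0.8 | 1.0 | 1.5 |
|---|---|---|---|---|---|
| subjects | 34 | 24 | 15 | 10 | 6 |

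Fifteen fits d of about 0.78 to 0.80. Nothing in the plan says that this was the test or the effect.

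**Step 2. Power within one subject.** Compare one paradigm with continuous stimulation, with r repeats each and error pooled over four paradigms. The error df are 4(r − 1), the noncentrality is δ√(r/2), and δ is the difference in within-subject SDs. The number of subjects appears in neither expression.

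- Standing, r = 3: df = 4 × 2 = 8 and critical t = 2.306. Power reaches 80% at δ = 2.61, where the noncentrality is 2.61 × √1.5 = 3.20. With Dunnett adjustment for three comparisons the critical value is about 2.88 and δ = 3.12.
- Power for r = 3, unadjusted: 19% at δ = 1, 58% at δ = 2 and 89% at δ = 3.
- Dynamometer, only if both legs count as r = 6 independent readings: df = 4 × 5 = 20 and critical t = 2.086, so δ = 1.70. With Dunnett the critical value is about 2.54 and δ = 1.97.

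These values are the same for 1, 15 or 25 subjects. They cannot be turned into minutes or torque, because the plan prints no within-subject SD.

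**Step 3. What 15 could detect across subjects.** Take a paired t-test on subject-level differences, with df = n − 1 and noncentrality d√n. At n = 15 the critical t is 2.145, and 80% power needs a noncentrality of 3.013, so d = 3.013/√15 = 0.78. At one third of 5%, for three paradigms, the critical t is 2.718 and d = 3.613/√15 = 0.93.

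| complete subjects | d at 5% | d at 5%/3 |
|---|---|---|
| 15 | 0.78 | 0.93 |
| 12 (illustration of loss) | 0.89 | 1.08 |
| 25 (15 new + 10 existing) | 0.58 | 0.69 |

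A one-sided 5% test with 15 would give 0.68. Steps 2 and 3 use different SDs (within one subject, and of differences between subjects), so their figures cannot be compared directly.

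**The case against.** The plan never says in one sentence that per-subject power fixed the 15. Item 10 ties 80% to effect sizes and does not mention 15; Item 11 ties 15 to three outcomes and does not mention per-subject tests. The 15 may rest on an across-subject calculation that was not printed. Analyses 1, 2 and 4 and the closing sentence of Item 10 name no unit, and neither do the stability change scores nor the comparison with previously implanted subjects in Item 13. Making the primary analyses individual does not rule out secondary group analyses. Fifteen replications of a single-subject experiment is also a legitimate design, and Item 11 asks only for a brief description.

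Much of this stands, and it is why the point says that no across-subject test is *clearly* specified. It does not remove the mismatch. If a group calculation lies behind the 15, its test is missing from Item 10. If replication is the reason, Item 11 should say so in place of a power level. The general sentence of Item 10 makes the primary analyses individual, and analysis 3, which covers two of the three sizing outcomes, is explicitly per subject.

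A reader might infer that 15 is too few, that the per-subject tests are inadequate, or that a figure was miscalculated. The documents support none of these. Without an effect size, SD or alpha, 15 may be ample or short. A difference of 2.6 within-subject SDs may be easy to reach if trials in one person vary little.

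**Conclusion.** The point holds as a mismatch between the stated basis for the sample size and the stated primary analyses. Fifteen cannot follow from 80% power for tests performed within each subject, and the plan does not clearly name a test from which it could follow.

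Under the assumptions above, the within-subject detectable difference is about 2.6 SDs for standing (3.1 with Dunnett). For the dynamometer it is about 1.7 (2.0 with Dunnett), and only if six readings from two legs count as independent. Fifteen complete subjects could detect a standardised paired difference of 0.78 (0.93 at 5%/3). The mismatch itself depends on none of these assumptions. It should be fixed, but it does not show the study to be undersized.

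**What to change.** 1. **Item 11.** Either name the across-subject test behind the 15, with its outcome, effect size, SD and alpha, or drop the power claim for the number of subjects and justify 15 as replication and generalizability, as Item 8 already does.

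2. **Item 10, units and per-subject power.** State the unit for analyses 1, 2 and 4 and for the closing sentence. Print the within-subject SD from the existing 8-channel users and the detectable difference that follows. Suggested text for standing tests only:

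> Assuming a two-sided 5% level, independent repeats and pooled error on 8 df, three repeats per paradigm give 80% power within one subject for a difference from continuous stimulation of 2.6 within-subject SDs (3.1 with Dunnett adjustment).

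   Give dynamometer tests their own sentence, saying whether the two legs are treated as independent.

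3. **Item 10, one added analysis.** Keep the per-subject analyses and add an across-subject paired contrast of each paradigm with continuous stimulation, on subject means of one named outcome such as elapsed standing time. The log scale is a reasonable choice for a positive duration. The skew that Item 8 reports is between subjects in an earlier cohort and does not by itself settle the scale. Use the 15 new subjects, and report the 10 existing recipients separately or as a sensitivity analysis. State that 15 complete subjects give 80% power for a standardised paired difference of 0.78, or 0.93 at 5%/3 for three paradigms, and that the figure is larger if fewer complete. Present this as what 15 can detect, not as how 15 was derived.

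The cost is some rewording and one extra analysis of data already planned, with no added subjects or sessions. The power statement for the per-subject tests becomes less favourable, and a log-scale result must be explained as a ratio of standing times.
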